7.2.8. Common Calculations

Each subject's age will be calculated based on their date of birth relative to the date of the screening visit. Where only a subject's year of birth is collected, their date of birth will be imputed with 30th June (30 Jun YYYY).

Body Mass Index (kg/m^2) = Weight $(kg)/Height (m)^2$.

The predicted normal FEV1 and reversibility values are recoded in the CRF as per the protocol assessment visits. The predicted normal FEV1 is based on the NHANES III equations as described in the protocol and Asian equation will be used for Asian race.

Reversible is defined as an increase in FEV1 of ≥12% and ≥200mL following administration of bronchodilator (albuterol/salbutamol) at any protocol assessment visit.

Non-reversible is defined as a post-bronchodilator (post-albuterol/salbutamol) increase in FEV1 of <200mL or increase that is <12% from pre-bronchodilator (pre-albuterol/salbutamol) FEV1.

A subject is considered achieved asthma control between Week 20 and Week 24 if he/she does not have a clinically significant exacerbation during this period between W20 and W24. The process for assessing clinically significant exacerbations of asthma is provided in Appendix9. Visit Windows.

Where a subject does not prematurely withdraw from the study, or the subject withdraws prematurely from the study at a scheduled visit, there are no plans to derive visit windows; visits will be used in the analyses as reported on the CRF.

For subjects prematurely withdrawing from the study, the EOS, unscheduled or IP discontinuation visit will initially be remapped to the next scheduled protocol specific assessment visit for each parameter, if the visit falls ±7 days of next scheduled planned visit (see below). Otherwise, the data will be remapped to the next planned scheduled visit. If there are more than one assessment associated with a particular visit interval, then the visit will be remapped to that with the closest target day. If subject having multiple records on same day for parameter (lab, ECG etc), then for continuous parameter data average value and for categorical parameter data, worst value will be presented. Please reframe the text accordingly.

| Visit | Target Day | Window (Days) |
|-------------------|------------|---------------|
| Visit 3 (Week 4) | 28 | 21 to 35 |
| Visit 4 (Week 8) | 56 | 49 to 63 |
| Visit 5 (Week 12) | 84 | 77 to 91 |
| Visit 6 (Week 16) | 112 | 105 to 119 |
| Visit 7 (Week 20) | 140 | 133 to 147 |
| Visit 8 (Week 24) | 168 | 161 to 175 |

Unless otherwise stated, unscheduled visits will be included in the data listings only. If an unscheduled visit is present because of a visit/assessment missed due to COVID-19 factors, the unscheduled assessment may be used for remapping. The unscheduled visits may be used for summaries related to 'any time post baseline' assessment.

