7.2.5. OCS Dose Reduction

Percent OCS Dose Reduction during Weeks 20 - 24 = 100 * (Baseline Dose – Maintenance Dose during Weeks 20 - 24)/Baseline dose.

Baseline dose is defined as the prescribed optimized prednisone/prednisolone dose following the OCS optimization run-in period and maintenance dose is defined as the mean average of all daily prednisone/prednisolone doses during the maintenance phase of Weeks 20 -24. The visit window for calculating OCS dose at each reporting period is described below:

| Reporting Period | First Day Included | Last Day Included |
|--------------------------------------|-------------------------|----------------------|
| Optimised Dose | N/A | N/A |
| Baseline – Week 4 | Day after Week 0 visit | Day of Week 4 visit |
| Week 4 – Week 8 | Day after Week 4 visit | Day of Week 8 visit |
| Week 8 – Week 12 | Day after Week 8 visit | Day of Week 12 visit |
| Week 12 – Week 16 | Day after Week 12 visit | Day of Week 16 visit |
| Week 16 – Week 20 | Day after Week 16 visit | Day of Week 20 visit |
| Maintenance Dose (Week 20 – Week 24) | Day after Week 20 visit | Day of Week 24 visit |
| | - | - |

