10.7. IMPUTATION OF MISSING DATA

Missing values will be treated as missing unless and otherwise specified. If a subject experience a clinically significant asthma exacerbation between Weeks 20-24, then for the purpose of assessing percentage of subjects achieving at least 50% reduction in OCS dose during the weeks 20-24, the subject will be imputed into the worst-case category of 'no reduction in OCS Dose'. For the analysis of median percent OCS reduction during weeks 20-24, the subject will be imputed using the maximum dose of OCS observed during the 4-Weekly period across all participating subjects.

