- Confidence intervals are displayed within round brackets and separated by a comma. The lower limit is presented first, and the upper limit is presented second. The confidence interval is placed either beside or below the corresponding estimate. The estimate and the confidence limits are presented using the same degree of precision.
- P-values will be output in the format: '0.xxx', where xxx is the value rounded to 3 decimal places. Every p-value less than 0.001 will be presented as <0.001. If the p-value is returned as >0.999, then present as >0.999.
- Percentage values will be printed to one decimal place. Unless otherwise noted, for all percentages, the number of subjects in the analysis population for the treatment group who have an observation will be the denominator. Percentages after zero counts will not be displayed and percentages equating to 100% will be presented as 100%, without decimal places.
- Tabular display of data for medical history, prior/concomitant medications, and all tabular displays of adverse event data will be presented by the body system, treatment class, or SOC with the highest occurrence in the active treatment group in decreasing order, assuming all terms are coded. Within the body system, drug class and SOC, medical history (by preferred term), drugs (Medication class), and adverse events (by preferred term) will be displayed in decreasing order. If incidence for more than 1 term is identical, they will then be sorted alphabetically.
- Missing descriptive statistics or p-values which cannot be estimated will be reported as '-' Missing values for numeric and character variables are displayed as blanks in data listings
- The percentage of subjects will normally be calculated as a proportion of the number of subjects assessed in the relevant treatment group (or overall) for the analysis population presented. However, careful consideration is required in many instances due to the complicated nature of selecting the denominator, usually the appropriate number of subjects exposed. Details will be described in footnotes or programming notes, as necessary.
- If no relevant data are available at all for a display, then present "No data to Report".

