APPENDIX 5. LIST OF TABLES, FIGURES AND LISTINGS

List of Tables

| Table | Table Title |
|-----------|--|
| Number | |
| 14.1.1.1 | Summary of Subject Disposition (Enrolled Population) |
| 14.1.1.2 | Summary of Reasons for Discontinuation (Safety Population) |
| 14.1.1.3 | Summary of Reasons for Screen or Run-in Failure (All Enrolled Population) |
| 14.1.1.4 | Summary of Inclusion, Exclusion and Induction Phase Criteria Deviations (Safety Population) |
| 14.1.1.5 | Summary of Important Protocol Deviations (Safety Population) |
| 14.1.1.6 | Summary of Important Protocol Deviations Leading to Exclusion to Treatment (Safety Population) |
| 14.1.1.7 | Summary of Important Protocol Deviations Related to COVID-19 Pandemic (Safety Population) |
| 14.1.1.8 | Summary of Visits Impacted by COVID-19 Pandemic (Safety Population) |
| 14.1.2.1 | Summary of Demographic Characteristics (Safety Population) |
| 14.1.2.2 | Summary of Asthma History and Baseline Disease Characteristics (Safety Population) |
| 14.1.2.3 | Summary of Asthma Exacerbation History (Safety Population) |
| 14.1.2.4 | Summary of Family History of Cardiovascular Risk Factors (Safety Population) |
| 14.1.2.5 | Summary of Medical Conditions (Safety Population) |
| 14.1.2.6 | Summary of Asthma Medications Taken by Treatment Period and Respiratory Medication Class |
| | (Safety Population) |
| 14.1.2.7 | Summary of Non-Asthma Concomitant Medications Taken During Treatment (Safety Population) |
| 14.1.2.8 | Summary of Screening, Run-in and Baseline Lung Function Results (Safety Population) |
| 14.1.3 | Summary of Treatment Exposure and Number of Study Drug Administration (Safety Population) |
| 14.2.1.1 | Analysis of Subject Achieved at least 50% Reduction in OCS Dose During Weeks 20-24 |
| 44.0.4.0 | Relative to Baseline, while Maintaining Asthma Control (Safety Population) |
| 14.2.1.2 | Summary of OCS Dose Categories During Weeks 20-24 (5 mg Cut-off) (Safety Population) |
| 14.2.1.3 | Summary of OCS Dose Category During Each Reporting Period (Safety Population) |
| 14.2.1.4 | Summary of Percent Change from Baseline OCS Dose Categories Relative to Baseline by Reporting Period (Safety Population) |
| 14.2.1.5 | Summary of OCS Dose (mg/day) and Change from Baseline During Each Reporting Period (Safety Population) |
| 14.2.1.6. | Summary of Median Percent OCS Dose (mg/day) Reduction During Weeks 20-24 While |
| | Maintaining Asthma Control (Safety Population) |

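### The visible SAP has no rule for withdrawals in the OCS-reduction outputs: those leaving before Week 20 drop out, and those leaving in Weeks 20-24 can count as successes on a few days of data

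*SAP*

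**What the plan says.** - **Control.** SAP 7.2.8: "A subject is considered achieved asthma control between Week 20 and Week 24 if he/she does not have a clinically significant exacerbation during this period". Being observed in the window is not a condition. SAP 7.2.6 ends the exacerbation assessment period at early withdrawal, so no later event can be recorded.
- **Dose.** SAP 7.2.5: "maintenance dose is defined as the mean average of all daily prednisone/prednisolone doses during the maintenance phase of Weeks 20 -24". The window runs from the day after the Week 20 visit to the day of the Week 24 visit, and no minimum number of days is given.
- **Missing data.** SAP 10.7 starts from "Missing values will be treated as missing unless and otherwise specified". Its exception applies "If a subject experience a clinically significant asthma exacerbation between Weeks 20-24". The participant is then placed in the no-reduction category for the responder analysis; for the median, "the subject will be imputed using the maximum dose of OCS observed during the 4-Weekly period across all participating subjects". Withdrawal is not a trigger.
- **Denominator.** The default in SAP 12, unless otherwise noted, is that "the number of subjects in the analysis population for the treatment group who have an observation will be the denominator".
- **Outputs.** Table 14.2.1.1 is titled "Analysis of Subject Achieved at least 50% Reduction in OCS Dose During Weeks 20-24" and adds the condition of maintained asthma control. Table 14.2.1.6 gives the median percent reduction under the same condition. Both are labelled Safety Population, whereas Protocol 4.2 limits the OCS-sparing assessment to participants who completed or withdrew before Amendment 4. Withdrawals are therefore part of the intended subset.

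**The concern.** The worst-case rule exists so that a low OCS dose is not credited when asthma control was lost. A completer who exacerbates in Week 22 is scored as no reduction. A participant who exacerbates in Week 18 and leaves in Week 19 for lack of efficacy (a withdrawal reason listed in Protocol 7.2) carries no penalty and disappears from the percentage. A participant who leaves in Week 21 on a reduced dose can be scored as a success. The rule thus catches failures seen inside the window and misses those that ended participation before or during it.

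Protocol 4.2 says the study will evaluate the OCS-sparing effect, and there is no comparator arm in which the same omission would occur. A favourable shift in these tables would pass straight into the reported result.

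**Working it through.** The documents give no expected response rate, withdrawal rate or subset size for these outputs, so there is no stated figure to reproduce. The check applies the visible rules to cases and then sizes the effect under assumptions.

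**Step 1. The rules applied case by case**

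| Participant | Control (7.2.8) | Week 20-24 dose (7.2.5) | Worst case (10.7) | Result |
|---|---|---|---|---|
| Completer, no event in window | met | full | no | scored on own dose |
| Completer, exacerbation in Week 22 | not met | full | yes | no reduction, stays in denominator |
| Exacerbation in Week 18, withdraws in Week 19 | met by default | none | no | missing, leaves denominator |
| Lost at Week 8 | met by default | none | no | missing, leaves denominator |
| Withdraws in Week 21 on at least 50% less OCS, no event | met | a few days | no | success |

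In the last row, the visit-window text in SAP 7.2.8 remaps an early-withdrawal visit to the next scheduled visit, here Week 24. The 7-day minimum in SAP Appendix 3 is for eDiary parameters, and its list does not name OCS dose. Protocol 8.1.4 does list daily OCS dose as an eDiary item. If the minimum is taken to apply, 7 days would still stand for a 28-day window.

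**Step 2. Responder rate, withdrawals before Week 20**

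Let p be the share with at least 50% reduction among those with a Week 20-24 dose, and w the share of the subset withdrawn before Week 20. Both are assumed.

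- Observed-only rate: p
- Withdrawals as failures: p(1 - w)
- Difference: p - p(1 - w) = p × w

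| w | Observed-only (p = 50%) | Withdrawals as failures | Difference |
|---|---|---|---|
| 5% | 50% | 47.5% | 2.5 points |
| 10% | 50% | 45.0% | 5.0 points |
| 15% | 50% | 42.5% | 7.5 points |

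For p of 40-60% and w of 5-15%, the range is 0.40 × 0.05 = 2 points to 0.60 × 0.15 = 9 points. Wider assumptions (p 30-70%, w 5-20%) give 0.30 × 0.05 = 1.5 to 0.70 × 0.20 = 14 points. If the whole subset is already the denominator, the reported rate is p(1 - w) and the difference is zero.

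**Step 3. The same in participants**

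Take an illustrative subset of 40, with 4 withdrawn before Week 20 and 18 responders among the 36 with a dose. Observed-only is 18/36 = 50%; with withdrawals as failures it is 18/40 = 45%. If one of the 18 was a Week 21 withdrawal scored on a partial window, reclassifying that participant gives 17/40 = 42.5%. That further 1/40 = 2.5 points is not removed by using the full denominator.

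**Step 4. Median reduction**

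If pre-Week-20 withdrawals are ranked worst, the median of the whole subset falls at quantile (0.5 - w)/(1 - w) of the observed reductions: 0.45/0.95 = 47th percentile at 5%, 0.40/0.90 = 44th at 10%, 0.35/0.85 = 41st at 15%. The documents do not allow this to be turned into a dose reduction.

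**The case against.** - **No visible rule turns a pre-Week-20 withdrawal into a success.** A reader might infer from the control definition that such participants are counted as OCS responders. They are not: both outputs also need a Week 20-24 dose, which they lack. This stands. The issue for them is the denominator; only withdrawals inside the window can become successes.
- **No control percentage is reported on its own.** A reader might also infer that the proportion controlled is overstated by the full withdrawal fraction. The literal definition would do that, but SAP Appendix 5 lists no stand-alone control table. This stands.
- **The denominator is not fixed.** The SAP 12 default yields to anything otherwise noted. A later item in that section calls for care, mentions the number exposed as usual, and leaves details to footnotes or programming notes. A missing category is also to be displayed. This stands in part: the bias is conditional, but a choice left to programming notes is not pre-specified in the SAP, and displaying participants as missing does not classify them.
- **The relevant text may have been removed.** The protocol's summary of changes says estimands were added for exploratory endpoints, and the exploratory entries in Protocol 3 and SAP 3.3 and 10.1.3 are absent from the public version. This stands as a caveat. SAP 10.7, however, is visible, deals with these two OCS analyses by name, and has no withdrawal rule.
- **The effect is small and the remedy is an estimand choice.** Protocol 7.2 expects withdrawal to be uncommon and asks sites to retain participants who stop treatment. With 40 participants at 50%, the 95% half-width is about 1.96 × √(0.25/40) = 15 points, larger than the shift. The SAP assumes missing at random after withdrawal for exacerbations and PEF, and failing every withdrawal would penalise some leaving for unrelated reasons. This is fair on size. On the choice, the SAP has already adopted a worst-case approach for these two outputs; the point is to apply it consistently and show the alternative.

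**Conclusion.** The concern holds in limited form. On the visible text, control in Weeks 20-24 does not require observation, the worst-case rule does not reach withdrawals, and partial windows have no stated minimum for OCS dose. Relative to counting withdrawals as failures, the responder rate in Table 14.2.1.1 is overstated by p × w: 5 points at 50% response and 10% withdrawal, and 2 to 9 points over the narrower assumed ranges. Partial-window successes come on top of this. The pre-Week-20 part is zero if the full OCS subset is the denominator. All response and withdrawal rates are assumptions.

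The effect is confined to two exploratory outputs in a pre-Amendment-4 subset of unstated size. No hypothesis is tested, and the primary safety endpoint and the secondary efficacy endpoints are untouched. The change is worth making before database lock because it is cheap and these are the visible outputs bearing on OCS sparing.

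**What to change.** First check the unredacted exploratory text. Unless it already settles these points:

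1. In SAP 7.2.8, define control as observed through the Week 24 visit with no clinically significant exacerbation between Weeks 20 and 24.
2. In SAP 10.7, extend the existing worst-case rule, for both the responder and the median analyses, to participants who withdraw before the Week 24 visit or have no Week 20-24 OCS dose.
3. State that the denominator for Tables 14.2.1.1 and 14.2.1.6 is all participants in the OCS subset of Protocol 4.2, and align the table labels with it.
4. Keep the observed-only result as a sensitivity analysis.

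The cost is a few sentences of SAP text and a small programming change, with no new data. The reported percentages will be slightly less favourable. Some withdrawals unrelated to asthma will be scored as failures; the sensitivity analysis shows how much that matters.

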7.2.10. MedDRA and WHO Drug Coding Versions

Where applicable, safety data will be coded using the following coding dictionaries:

| Dictionary | Version |
|---|---------------|
| Medical Dictionary for Regulatory Activities (MedDRA) | 26.0 |
| World Health Organization Drug Dictionary (WHO-DD) | March 2020 B3 |

7.2.11. Software Version

All analyses will be conducted using SAS version 9.4 or higher.

8. INTERIM ANALYSIS

No interim analysis is planned for this study.

9. SUBJECT CHARACTERISTICS AND STUDY CONDUCT SUMMARIES

9.1. SUBJECT DISPOSITION

Subject disposition table will be summarized based on the safety population. The following summaries

will be included in the disposition table:

- Total number of subjects enrolled in the study
- Total number of subjects screen failure
- Total number of subjects re-screened
- Total number of subjects passed screen but not received the treatment
- Total number of subjects in safety population
- Number of subjects who completed the study treatment
- Number of subjects who completed the study
- Number and percentage of subjects who discontinued from the study
- Number and percentage of subjects who pre-maturely discontinued the treatment as well as from the study along with reason for discontinuation.

Percentages will be based on the number of subjects in the safety population or enrolled population. Number and percentages of the reasons for study discontinuation is based on the total discontinued subjects.

A summary of reasons for screen failure, rescreen and the number of subjects included in the analysis population (Safety) will be presented based on all enrolled population. The percentages will be based on the number of subjects in all enrolled population.

In addition, the following summaries will be generated based on the safety population:

- Summary of inclusion, exclusion and induction phase criteria deviations
- Summary of important protocol deviations
- Summary of important protocol deviations related to COVID-19 pandemic
- Summary of visits impacted by COVID-19 pandemic

A by-subject listing of disposition will be provided for all enrolled population.

9.2. DEMOGRAPHIC AND BASELINE CHARACTERISTICS

Subjects' demographics and baseline characteristics will be summarized for the safety population.

Continuous variables (e.g., age and weight) will be summarized using descriptive statistics (n, mean, standard deviation, median, minimum, and maximum). Qualitative variables (e.g., sex and race) will

be summarized with counts and percentages.

The demographic parameters will include age, gender race height, weight and body mass index. Age will also be presented as a categorical variable (18-29 years, 30-49 years, 50-64 years and >=65 years). The baseline characteristics include:

- Asthma history and baseline disease characteristics which includes smoking history (never, current and former), age at onset (years) asthama diagnosis, time since diagnosis, asthma duration categories (1 to <5 years, 5 to <10 years, 10 to <15 years, 15 to <20 years, 20 to <25 years and >=25 years), experienced exacerbations in the previous 12 months, optimized OCS dose, duration of OCS dose prior to screening. Baseline optimized OCS dose also presented as a categorical variable (<7.5 mg/day, 7.5 to <15 mg/day, 15 to <30 mg/day and >=30 mg/day).
- Asthma exacerbations history which includes number of exacerbations (both descriptive and categorical), exacerbation types and causes of exacerbations in the previous 12 months.
- Family history of cardiovascular risk factors
- Past and current medical conditions
- Lung function test results at screening and baseline which includes pre- and post-bronchodilator FEV₁ (L), pre-bronchodilator percent predicted FEV₁ (%), pre-bronchodilator forced vital capacity (FVC) (L), reversibility (in mL and in %) and pre-bronchodilator FEV1/FVC.

By-subject listings of demographic and baseline characteristics will be provided for the safety populations.

9.3. MEDICATIONS

Medications will be coded using the latest available version of the Anatomical Therapeutic Chemical (ATC) classification text from the World Health Organization Drug Dictionary (WHO DD) and summarized separately for asthma and non-asthma medications. Asthma related medications will be presented by respiratory medication class and treatment period (prior treatment, on- treatment and post-treatment) and non-asthma related medications will be reported by ATC1 class and preferred name ingredients only for on-treatment period (concomitant). A by-subject listing of asthma and non-asthma medications will be provided for the safety population.

Medication that was started in the run-in period and stopped/continued during the on-treatment (concomitant) period will be included in both pre- treatment and on-treatment (concomitant) period summaries.

10. STATISTICAL ANALYSIS

All analyses of safety data and efficacy data will be generated for the Safety Population. All p values and 2-sided confidence intervals will be considered nominal without multiplicity control. Additionally, separate subgroup analyses will also be generated by with/without baseline maintenance OCS use (with separate summaries in those participants receiving maintenance OCS at baseline and those not maintenance OCS at baseline).

